## 5 Study Treatments

### 5.1 Method of Assigning Patients to Treatment Groups

Severe CKD patients (Cohort 1) and HD patients (Cohort 2) will receive a single dose of 0.5 mg KBP-5074. A total of 6 patients will be assigned to each of Cohorts 1 and 2.

Each patient will be assigned a screening number. Once enrolled into the study, patients will be assigned a unique patient number starting with a 2 digit site number, followed by a unique 3 digit patient number.

Patients who replace discontinuing patients after the first study drug administration has taken place will be assigned the number of the discontinued patient +500 (eg, Patient 01101 will be replaced by Patient 01601, Patient 02202 will be replaced by Patient 02702).

### 5.2 Treatments Administered

All doses of KBP-5074 will be administered orally to patients at the CRU. Administration of each dose of study drug will be supervised, verified (see [Section 5.7](#)), and documented according to the CRU's standard operating procedures. The actual date and time of each dose administration will be entered in the eCRF.

In Part 1 of the study, non-HD patients with severe CKD in Cohort 1 will receive a single oral capsule dose of 0.5 mg KBP-5074 with up to 240 mL of room temperature water on Day 1 following a fast between 2 and 4 hours. The exact amount of water consumed will be recorded in the eCRF.

In Part 2 of the study, HD patients with severe CKD will receive a single 0.5 mg oral capsule dose of KBP-5074 with up to 240 mL of room temperature water following a fast between 2 and 4 hours. The exact amount of water consumed with the dose of KBP-5074 will be recorded in the eCRF. The dose of KBP-5074 will be administered on Day 1 immediately following a dialysis session.

### 5.3 Identity of Investigational Product

The Sponsor (KBP Biosciences Co., Ltd.) will provide adequate supplies of KBP-5074 for use during the study as shown in [Table 5-1](#).

**Table 5-1 Investigational Product**

	KBP-5074	
Strength	0.5 mg	
Formulation	Capsules	
Supplier/ manufacturer	KBP Biosciences Co., Ltd. [name] [name]	Frontage Laboratories, Inc. [name] [name]

## **5.4 Management of Clinical Supplies**

### **5.4.1 Study Drug Packaging and Storage**

KBP-5074 capsules, 0.5 mg are packaged in high-density polyethylene (HDPE) bottles and sealed with aluminum foil.

KBP-5074 capsules, 0.5 mg must be stored at room temperature in tightly closed containers and protected from light. Doses of KBP-5074 will be prepared and dispensed by qualified CRU staff.

### **5.4.2 Test Article Accountability**

The Investigator will maintain accurate records of receipt of all test articles, including dates of receipt. In addition, accurate records will be kept regarding when and how much test article is dispensed and used by each patient in the study. Reasons for departure from the expected dispensing regimen must also be recorded. At the completion of the study, to satisfy regulatory requirements regarding drug accountability, all study drugs will be reconciled and retained or destroyed according to applicable regulations.

## **5.5 Overdose Management**

An overdose is any dose of study treatment given to a patient or taken by a patient that exceeds the dose described in the protocol. Any overdose, with or without associated AEs, must be promptly reported to the Investigator. Overdoses without signs or symptoms do not need to be recorded as AEs; in case of any AEs associated with the overdose, these should be reported on relevant AE/SAE sections in the eCRF.

### **5.5.1 Treatment of Overdose**

In the event of suspected overdose, the appropriate supportive clinical care should be instituted at the discretion of the Investigator or as dictated by the patient's clinical status.

## **5.6 Blinding**

This is an open-label study and no blinding procedures will be used.

## **5.7 Treatment Compliance**

Each dose of study drug will be administered by delegated study staff under direct medical supervision of the Investigator. A hand and mouth check will be performed immediately after each study drug administration to verify that the study drug was swallowed. The determination of plasma concentrations of KBP-5074 during the analytical phase will provide further confirmation of treatment compliance.

## **5.8 Prior and Concomitant Therapy**

Prior medications will be collected within 30 days prior to KBP-5074 dosing on Day 1. Use of all concomitant medications will be recorded in the patient's eCRF. The minimum requirement is that drug name and the dates of administration are to be recorded. This will include all prescription drugs, herbal products, vitamins, minerals, and over-the-counter medications. Any changes in concomitant medications also will be recorded in the patient's eCRF.

Any concomitant medication deemed necessary for the welfare of the patient during the study may be given at the discretion of the Investigator. However, it is the responsibility of the Investigator to ensure that details regarding the medication are recorded in full in the eCRF.

### **5.8.1 Permitted Therapy**

Concomitant therapy includes all medications and non-medication interventions used by a patient starting from 4 weeks prior to the first dosing through the end of study assessment. Medications include prescription drugs, over-the-counter drugs, approved dietary and herbal supplements, and nutritional supplements; examples of non-medication interventions include individual psychotherapy, cognitive behavioral therapy, smoking cessation therapy, and rehabilitative therapy. All concomitant medications and non-medication interventions should be reported to the Investigator and recorded in the concomitant medications eCRF.

As a general rule, no concomitant medication will be permitted unless the rationale for use is discussed between the Investigator and the Sponsor, and is clearly documented. The following medications are exceptions:

- Medications used to treat AEs may only be prescribed after consultation with the Medical Monitor (with the exception of acetaminophen and paracetamol), unless there is an immediate medical need to ensure the well-being of the patient that should

not be delayed. All therapy and/or medication administered to manage AEs should be recorded in the AE eCRF.

- Hormone replacement therapy: continue using if initiated at least 2 months prior to the first dose of study drug.
- Acetaminophen and paracetamol is allowed at a maximum dose of 2 g per day up to 48 hours prior to dosing. During the confinement period at the CRU, patients will be restricted from the use of acetaminophen and paracetamol and other non-prescription medications beginning 4 hours prior to study drug administration through 4 hours after study drug dosing, unless deemed necessary to treat an AE by the Investigator.
- Patients requiring HD may continue to receive routine medications to maintain their stable medication regimen.

### **5.8.2 Prohibited Therapy**

Prohibited medications include but are not limited to:

- Any other investigational drug taken within 30 days or 5 half-lives (whichever is longer) prior to the dose of study drug on Day 1.
- Patients will refrain from taking MRAs (eg, spironolactone, eplerenone) or potassium sparing diuretics (eg, amiloride, triamterene).
- Use of or treatment with any prescription drugs, herbal products, vitamins, minerals, and over-the-counter medications within 14 days prior to Check-in (Day -1) and during the study. Exceptions may be made on a case by case basis following discussion and agreement between the Investigator and the Sponsor. Patients requiring HD (Part 2) may continue to receive routine medications (including vitamins, antidepressants, antihypertensive, and low dose aspirin) to maintain their stable medication regimen.
- Use of any nutrients known to modulate CYP3A activity (based on the KBP-5074 metabolic pathway) or any strong or moderate inhibitors or inducers of CYP3A4, starting from 14 days prior to dose administration on Day 1 until the final end of study assessments, including but not limited to the following: inhibitors such as ketoconazole, miconazole, itraconazole, fluconazole, atazanavir, erythromycin, clarithromycin, ranitidine, cimetidine, verapamil, and diltiazem and inducers such as rifampicin, rifabutin, glucocorticoids, carbamazepine, phenytoin, phenobarbital, and St. John's wort.

- Unless part of an established, stable medication regimen for patients requiring HD, any prescribed or over-the-counter medications, are prohibited within 2 weeks prior to the first dosing until the final end of study assessment.

## **5.9 Diet, Fluid, and Activity Control**

Patients will refrain from strenuous exercise from 48 hours prior to Check-in (Day -1) or during the study through the final end of study assessment.

Doses of KBP-5074 will be administered with up to 240 mL of room temperature water. Patients will be required to abstain from consuming water from 1 hour prior to dosing of KBP-5074 and for 1 hour postdose. At all other timepoints, patients may consume water on an ad libitum basis.

Light smoking (fewer than 10 cigarettes per day) is permitted during the study.

During confinement at the CRU, patients will receive standardized meals. Meals or snacks may be provided to patients requiring HD as needed per the Investigator's discretion.

Patients will be advised to maintain their normal diet and not consume alcohol or potassium-rich foods or drinks during the study period.

## **6 Study Assessments and Procedures**

Before performing any study procedures, all potential patients will sign an informed consent form (ICF). Patients will have the opportunity to have any questions answered before signing the ICF. The Investigator must address all questions raised by the patient.

The study assessments to be performed at each visit and timepoint are specified in separate schedules for each part of the study. The schedule of events for Part 1 and Part 2 are presented in [Table 12-1](#) and [Table 12-2](#), respectively.

### **6.1 Safety and Tolerability Assessments**

The safety and tolerability of KBP-5074 will be assessed by evaluation of AEs, physical examinations, vital sign measurements, ECGs, and clinical laboratory parameters (hematology, clinical chemistry, and urinalysis). Additional safety assessments may be performed as needed at the discretion of the Investigator. Safety assessments will be performed at scheduled intervals from Day 1 through the end of study assessment.

### **6.1.1 Body Height, Weight, and BMI**

At Screening, body height (centimeters) and weight (kilograms) will be measured, and BMI will be calculated ( $\text{BMI} [\text{kg}/\text{m}^2] = \text{body weight} [\text{kg}] / \text{height}^2 [\text{m}^2]$ ).

### **6.1.2 Physical Examinations**

Full physical examinations include, at a minimum, assessment of the following systems: skin, head, ears, eyes, nose, and throat, respiratory system, cardiovascular system, gastrointestinal system, neurologic condition, blood and lymphatic systems, and the musculoskeletal system. A licensed physician or qualified designee will conduct the examinations.

Brief physical examinations include, at a minimum, assessment of the following systems: skin, head, eyes, and throat, chest and heart auscultation, abdominal examination, neurologic condition (ie, alert and oriented x3; not including cranial nerves), and edema assessment. A licensed physician or qualified designee will conduct the examinations.

Physical examinations may be performed at various unscheduled time points if deemed necessary by the Investigator. Symptom-directed physical examinations will be performed as appropriate for patients experiencing AEs.

Medical history and demographic data, including name, sex, age, race, and use of alcohol and tobacco, will be recorded at Screening.

### **6.1.3 Vital Sign Measurements**

Vital sign measurements will include systolic blood pressure, diastolic blood pressure, pulse rate, respiration rate, and body temperature and will be performed at the timepoints specified in [Table 12-1](#) and [Table 12-2](#) for Part 1 and Part 2, respectively. The allowable window for vital signs to be measured with respect to their nominal timepoint is -60 minutes for predose vital sign measurements and  $\pm 30$  minutes for postdose vital sign measurements.

Patients will remain at rest in a semi-recumbent position for a minimum of 5 minutes before vital sign measurements are obtained. For all patients, blood pressure and pulse rate will be measured using an automated sphygmomanometer. A confirmatory repeat vital sign measurement may be performed at the discretion of the Investigator. If other procedures are scheduled at the same timepoint, vital signs will be obtained first, before an ECG and/or blood draw.

### 6.1.4 12-Lead Electrocardiograms

Electrocardiogram parameters of ventricular rate, PQ or PR interval, QRS duration, QT interval (uncorrected), and QT interval corrected for heart rate according to Fridericia's formula (QTcF) will be performed at the timepoints specified in [Table 12-1](#) and [Table 12-2](#) for Part 1 and Part 2, respectively.

Electrocardiograms will be obtained with the patient remaining in a semi-recumbent position following 5 minutes of rest. If other procedures are scheduled at the same timepoint, the ECG should be obtained after vital sign measurements and/or before the scheduled blood draw. The allowable window for ECGs to be obtained with respect to their nominal timepoint is -60 minutes for predose ECGs and  $\pm 30$  minutes for postdose ECGs.

For all patients, ECGs will be reviewed, signed, and dated by the Investigator or a qualified designee. The ECGs will be classified as being one of three categories: normal, abnormal but not clinically significant (NCS), or abnormal and CS. All CS findings will be reported as AEs.

### 6.1.5 Clinical Laboratory Tests

Laboratory measurements (including hematology, clinical chemistry, and urinalysis) will be performed at the timepoints specified in [Table 12-1](#) and [Table 12-2](#) for Part 1 and Part 2, respectively. Clinical laboratory parameters for analysis are presented in [Table 6-1](#).

Serum potassium levels of study patients will be closely monitored throughout this study. To ensure quick access to laboratory results, serum potassium levels will be tested in local laboratories in this study. If serum potassium is  $>5.6$  mmol/L during a scheduled/unscheduled visit, serum potassium levels should be repeated as early as feasible (no more than 48 hours). For patients who currently take potassium supplementation, it is recommended that the repeat test of serum potassium be taken 24 hours after the stopping of potassium supplementation if the Investigator considers it clinically safe and feasible.

A single repeat of laboratory testing at Screening and Day -1 are allowed to rule out lab error (i.e. hemolysis in potassium specimens).

Urine or serum pregnancy tests (all female patients) and FSH tests (postmenopausal female patients) will be performed at the timepoints specified in [Table 12-1](#) and [Table 12-2](#) for Part 1 and Part 2, respectively.

An alcohol breath test and drug screen will be administered to all patients at the timepoints specified in [Table 12-1](#) and [Table 12-2](#) for Part 1 and Part 2, respectively.

**Table 6-1 Clinical Laboratory Parameters**

Chemistry Panel	Hematology	Urinalysis
Alanine aminotransferase	Hematocrit	pH
Albumin	Hemoglobin	Specific gravity
Alkaline phosphatase	Red blood cell count	Protein
Aspartate aminotransferase	Quantitative platelet count	Glucose
Bilirubin	White blood cell count	Ketones
Blood urea nitrogen	with differential (total and %):	Bilirubin
Calcium	Neutrophils	Blood
Chloride	Lymphocytes	Nitrite
Cholesterol	Monocytes	Urobilinogen
CO 2	Eosinophils	Leukocyte esterase
Creatinine	Basophils	
Gamma-glutamyltransferase		
Glucose	Other Tests	Drug Screen
Iron	HIV	Alcohol test –Breathalyzer
Lactate dehydrogenase	HbsAg	Drug screen: a
Phosphorous	HCV	Cocaine
Potassium	Pregnancy test (female patients)	Amphetamines
Protein	FSH (postmenopausal female	Barbiturates
Sodium	patients)	Benzodiazepines
Triglycerides		Opiates
Uric acid		Methadone

Abbreviations: FSH = follicle stimulating hormone; HbsAg = hepatitis B surface antigen; HCV = hepatitis C virus; HIV = human immunodeficiency virus.

a For patients in Part 1, a urine or salivary drug test will be performed at Screening and Check-in (Day -1). Hemodialysis patients in Part 2 will be tested with a serum drug screen at Screening and using salivary testing at Check in (Day -1).

### 6.1.5.1 Sample Collections

Instructions regarding the collection, processing, and shipment of laboratory samples is detailed in a separate laboratory manual. All samples will be given a unique identifier. The exact clock time of dosing, as well as actual sample collection date and time will be entered on the eCRF.

After all of the PK samples from a single patient have been collected and frozen at  $-70^{\circ}\text{C}$  or colder, the primary samples from each time point can be batched together with corresponding primary samples from other patients and carefully packaged and shipped frozen at  $-70^{\circ}\text{C}$  or colder to the bioanalytical laboratory designated by the Sponsor. Samples are to be shipped with sufficient dry ice to remain frozen during overnight transit. For each patient and time point, the remaining stored aliquots will be retained on site at  $-70^{\circ}\text{C}$  or colder until released or requested by the Sponsor.

### **Pharmacokinetic Blood Collection and Processing**

Blood samples for the PK analysis of KBP-5074 will be collected at the timepoints specified in [Table 12-1](#) and [Table 12-2](#) for Part 1 and Part 2, respectively. In Part 1, all blood samples will be taken by either direct venipuncture or an indwelling cannula inserted in a forearm vein. In Part 2, blood samples will be taken by either direct venipuncture or an indwelling cannula inserted in a forearm vein during the interdialytic interval and following HD. While HD patients are undergoing dialysis treatment, blood samples must be drawn from the predialyzer (inlet [arterial line]) and postdialyzer (outlet [venous line]) at the timepoints specified in [Table 12-2](#). Blood samples will be collected into labeled tubes containing sodium heparin.

In Part 2, serial PK samples will initially be collected during the postdose interdialytic interval (through approximately 44 hours postdose). Approximately 44 hours following dose administration, the next dialysis session will occur. Serial blood samples (inlet and outlet) as well as dialysate samples will be collected for the duration of this dialysis session (from approximately 44 hours postdose through approximately 48 hours postdose). Additional serial PK samples will be collected following this dialysis session through 312 hours postdose (see [Table 12-2](#)).

Immediately after the sample is collected, the tube should be gently inverted 5 to 8 times to thoroughly mix the anticoagulant and then placed upright in a cryoblock or test tube rack surrounded by ice until centrifugation. Samples will be centrifuged at  $1500 \times g$  for 10 minutes at approximately  $4^{\circ}\text{C}$  within 30 minutes of collection. The resultant plasma will be divided into 2 equal aliquots, placed in individual cryovials, and immediately frozen at  $-70^{\circ}\text{C}$  or colder within 1 hour of collection. The samples will be kept frozen at  $-70^{\circ}\text{C}$  or colder pending shipment to the bioanalytical laboratory. Additional details, including the acceptance of shipments by the bioanalytical laboratory, will be provided in a separate laboratory manual.

### **Dialysate Collection and Processing**

Dialysate will be collected for HD patients in Part 2 only. Pooled dialysate samples will be collected during specific intervals as specified in [Table 12-2](#). Sample aliquots of the dialysate will be collected and frozen at  $-70^{\circ}\text{C}$  or colder and the total volume of the collected dialysate will be recorded. The samples will be kept frozen at  $-70^{\circ}\text{C}$  or colder pending

shipment to the bioanalytical laboratory. Additional details, including the acceptance of shipments by the bioanalytical laboratory, will be provided in a separate laboratory manual. DaVita Clinical Research will document the make and model of the dialyzer, blood flow, and dialysate flow for this study.

## **6.1.6 Adverse Events**

### **6.1.6.1 Definitions of Adverse Events**

The Investigator is responsible for reporting all AEs that are observed or reported during the study, regardless of their relationship to study drug or their clinical significance.

An AE is defined as any untoward medical occurrence in a patient enrolled into this study regardless of its causal relationship to study drug. Patients will be instructed to contact the Investigator at any time after signing the ICF until the final end of study assessment if any symptoms develop.

A treatment-emergent AE (TEAE) is defined as any event not present before exposure to study drug or any event already present that worsens in either intensity or frequency after exposure to study drug.

An SAE is defined as any event that results in death, is immediately life threatening, requires inpatient hospitalization or prolongation of existing hospitalization, results in persistent or significant disability/incapacity, or is a congenital anomaly/birth defect. Important medical events that may not result in death, be life threatening, or require hospitalization may be considered SAEs when, based upon appropriate medical judgment, they may jeopardize the patient or may require medical or surgical intervention to prevent one of the outcomes listed in this definition. Examples of such medical events include allergic bronchospasm requiring intensive treatment in an emergency room or at home, blood dyscrasias or convulsions that do not result in inpatient hospitalization, or the development of drug dependency or drug abuse.

### **6.1.6.2 Eliciting and Documenting Adverse Events and Serious Adverse Events**

Adverse events and SAEs will be assessed from the time the patient signs the informed consent form until exit from the study.

At every study visit, patients will be asked a standard nonleading question to elicit any medically related changes in their well-being. They will also be asked if they have been hospitalized, had any accidents, used any new medications, or changed concomitant medication regimens (both prescription and over-the-counter medications).

In addition to patient observations, AEs will be documented from any data collected on the AE page of the eCRF (eg, laboratory values, physical examination findings, ECG changes) or identified from review of other documents (eg, patient diaries) that are relevant to patient safety.

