### 1.3 Summary of Clinical Studies

As of 31-March-2016, one clinical study (Protocol #: KBP5074-1-001, NCT02228733) has been completed and evaluated the safety, tolerability, and pharmacokinetics (PK) of KBP-5074 single dose administration in healthy male and female subjects. This was an open-label, parallel-group, single ascending dose study with a food effect panel. A total of 46 subjects received KBP-5074 at dose levels of 0.5, 1.0, 5, 10, and 30 mg in the fasting state and 10 mg in the fed state.

KBP-5074 was safe and well tolerated in healthy male and female subjects. There were no drug related adverse events (AE) reported during the study. There were no clinically meaningful trends noted based on safety laboratory assessments including the complete blood count and potassium levels, physical examinations, vital sign measurements or electrocardiograms (ECGs) during this study. No evidence of bone marrow suppression was observed with increasing drug exposure. Specifically, no clinically meaningful trends of the complete blood counts, (white blood cell, neutrophils, red blood cell, or platelets) with increasing drug exposure were observed. No gender difference of drug exposure was observed.

At the dose levels tested, the mean maximum concentration ( $C_{max}$ ) ranged from 9.37 ng/mL (0.5 mg) to 259.4 ng/mL (30 mg), area under the concentration-time curve from time 0 until 24 hours postdose ( $AUC_{0-24h}$ ) ranged from 162.5 ng\*hr/mL (0.5 mg) to 5016 ng\*hr/mL (30 mg), and area under the concentration-time curve extrapolated to infinity ( $AUC_{0-\infty}$ ) increased from 678.4 ng\*hr/mL (0.5 mg) to 28195 ng\*hr/mL (30 mg). The time to maximum concentration ( $t_{max}$ ) under fasted conditions varied from 4 to 7 hours suggesting relatively fast absorption of KBP-5074 following oral administration under fasted conditions. The average half-life is greater than 50 hours.

There is an ongoing clinical study (Protocol #: KBP5074-1-002, NCT02653014) that will assess the safety, tolerability, and PK of KBP-5074 multiple dose administration in healthy adults and subjects with mild to moderate CKD (defined as estimated glomerular filtration rate [eGFR]  $\geq 30$  and  $\leq 89$  mL/min/1.73 m^2).

Additional information regarding the clinical evaluation of KBP-5074 can be found in the IB.

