## **4.2 Withdrawal of Patients from the Study**

The duration of the study is defined for each patient as the date signed written informed consent is provided through the end of study assessment, which will be on Day 14 for Part 1 and Part 2 or the date of Early Termination (ET) for patients who are withdrawn prior to the end of study assessment.

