### **4.2.1 Reasons for Withdrawal/Discontinuation**

Patients may withdraw from the study at any time and for any reason without prejudice to their future medical care by the Investigator or at the study site. Every effort should be made to keep patients in the study. The reasons for patients not completing the study will be recorded. A patient may be withdrawn from the study for any of the following reasons:

1. Does not meet the protocol inclusion or exclusion criteria.
2. Noncompliance with the protocol.
3. A serious or intolerable AE that in the Investigator's opinion requires withdrawal from the study, including but not limited to laboratory safety assessments that reveal CS hematological or biochemical changes from the baseline values and symptoms or an intercurrent illness that justifies withdrawal.
4. Lost to follow-up.
5. Other (eg, pregnancy, development of contraindications of use of study drug).

6. The patient withdraws consent, or the Investigator or Sponsor decide to discontinue the patient's participation in the study.
7. The Investigator will also withdraw a patient if KBP Biosciences Co., Ltd. terminates the study.

Upon occurrence of a serious or intolerable AE, the Investigator will confer with the Sponsor. If a patient is discontinued because of an AE, the event will be followed until it is resolved. Any patient may withdraw his or her consent at any time.

Patient safety will be closely monitored throughout the study and the study will be conducted following GCP. All safety data and any available PK data will be reviewed after each cohort for Part 1 and Part 2 of the study to ensure patient safety. The entire study may be stopped at any time at the discretion of the Investigator in consultation with KBP Biosciences Co., Ltd.

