#### **4.2.2 Handling of Withdrawals**

Patients are free to withdraw from the study or study treatment at any time upon request. Patient participation in the study may be stopped at any time at the discretion of the Investigator or at the request of the Sponsor.

Patients who discontinue study treatment or active participation in the study will no longer receive study drug. When a patient withdraws from the study, the reason(s) for withdrawal shall be recorded by the Investigator on the relevant page of the electronic case report form (eCRF). Whenever possible, all patients who discontinue study treatment or withdraw from the study prematurely will undergo all end-of-study assessments at the time of ET. Patients who fail to return for final assessments will be contacted by the site in an attempt to have them comply with the protocol. Methods for follow up will consist of 2 documented phone calls followed by 1 registered letter.

It is vital to obtain follow-up data on any patient withdrawn because of an AE or serious adverse event (SAE). In every case, efforts must be made to undertake protocol-specified, safety, follow-up procedures.

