### **6.1.6.6 Follow-Up of Patients Reporting Adverse Events**

All AEs must be reported in detail on the appropriate page of the eCRF and followed to satisfactory resolution, until the Investigator deems the event to be chronic or not CS, or until the patient is considered to be stable.

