Blood samples for the determination of KBP-5074 concentrations and corresponding PK analysis will be collected at the following time points (All PK samples will be collected within  $\pm 5$  minutes of the nominal time unless otherwise specified): predose (at time 0 [-5 min], collected immediately prior to dosing) and 2, 4, 6, 8, 10, 12, 18, 24, 48, 72, 96, 120, 168, 216, 264, and 312 hours post dose.

Serum and plasma samples for biomarkers (aldosterone and serum potassium) will be collected at the following time points (All biomarker samples will be collected within  $\pm 5$  minutes of the nominal time unless otherwise specified): predose (at time 0 [-5 min], collected immediately prior to dosing) and 2, 6, 12, 24, 48, 72, 96, 120, 168, 216, 264, and 312 hours post dose.

Urine or salivary drug test performed at Screening and Check-in (Day -1).

Alcohol test (via Breathalyzer) is performed at Check-in (Day -1).

For female patients, urine or serum pregnancy test must be negative to enroll in the study. Patients who have a false positive test attributable to their post-menopausal state or kidney disease, as determined by the Investigator, will be allowed to participate.

End-of-study assessment will be performed after PK blood draw on Day 14 or upon withdrawal/dismissal of a patient from the study.

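### A dosed patient who leaves early for a reason other than an adverse event has no scheduled search for new AEs or SAEs over the rest of the planned 13 days

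*Protocol*

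**What the plan says.** The collection window is set in Section 6.1.6.2: "Adverse events and SAEs will be assessed from the time the patient signs the informed consent form until exit from the study". The Synopsis and Section 3.1 say the same. Section 4.2 defines how long each patient is in the study: from consent to the Day 14 assessment, "or the date of Early Termination (ET) for patients who are withdrawn prior to the end of study assessment". Section 4.2.2 asks that, whenever possible, patients who leave early "will undergo all end-of-study assessments at the time of ET". Footnote 11 of Table 12-1 agrees: "End-of-study assessment will be performed after PK blood draw on Day 14 or upon withdrawal/dismissal of a patient from the study". Footnote 13 of Table 12-2 repeats this for Part 2. Section 6.1.6.1 tells patients to report symptoms up to the final assessment.

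Other text provides some follow-up after withdrawal:

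- Section 4.2.1: when an AE causes discontinuation, "the event will be followed until it is resolved".
- Section 4.2.2 treats follow-up data as vital for patients withdrawn because of an AE or SAE. It also asks for efforts, in every case, to carry out the safety follow-up procedures that the protocol specifies.
- Section 6.1.6.3 requires all AEs to be followed to adequate resolution.
- Section 6.1.6.6 requires follow-up to satisfactory resolution, or "until the Investigator deems the event to be chronic or not CS, or until the patient is considered to be stable".

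Each patient receives one dose (Section 5.1), and follow-up is planned for 13 days after it (Section 3.1). On the drug's persistence, Section 1.3 says of healthy subjects: "The average half-life is greater than 50 hours".

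**The concern.** In a single-dose study, leaving early does not reduce exposure, because the only dose has already been given. What leaving early changes is how long anyone looks for its effects. The AE window is tied to exit and exit to the ET date, so a patient who leaves on Day 2 or 3 is actively observed for one or two days instead of 13.

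Safety and tolerability form a primary objective (Section 2.1). The Safety Population keeps everyone who received study drug (Section 7.5), and AEs are reported as numbers and percentages of patients (Section 7.7.2). A patient observed for a day or two therefore counts in the denominator like one observed for 13 days. The shortfall can only miss events; it cannot add them.

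Such exits are foreseeable. Section 4.2.1 lists failure to meet the entry criteria, noncompliance, and an investigator or sponsor decision. Section 10.2.2 says that major deviations, which can include breach of an entry criterion, will lead to withdrawal. A patient found ineligible after dosing would then leave scheduled safety observation, although the reason for ineligibility may itself bear on risk.

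**Working it through.** The protocol gives no figure of its own on this point, so there is nothing to reproduce. The check has three parts.

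**1. Who is left uncovered after ET.** Taking the withdrawal reasons in Section 4.2.1 in turn:

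- *AE or SAE:* the causal event is followed (Sections 4.2.1, 4.2.2, 6.1.6.3 and 6.1.6.6).
- *Lost to follow-up:* Section 4.2.2 already requires two documented calls and a registered letter.
- *Pregnancy:* followed to outcome even after discontinuation (Section 6.3).
- *Consent withdrawn:* contact may not be possible.
- *Ineligibility, noncompliance, major deviation, investigator or sponsor decision:* the patient may be fully contactable, but the protocol schedules no later safety contact. The request in Section 4.2.2 for follow-up efforts points to procedures the protocol specifies, and Tables 12-1 and 12-2 contain none after ET.

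The gap lies in the last group.

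**2. How much exposure can fall after exit.** Inputs are the 0.5 mg values in healthy subjects (Section 1.3): AUC0-24h = 162.5 and AUC0-∞ = 678.4 ng·h/mL.

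- Share by 24 h: 162.5 / 678.4 = 24.0%.
- Share after 24 h, when Part 1 patients leave the unit: 100% − 24.0% = 76.0%.

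Beyond 24 h I assume mono-exponential decline:

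R(t) = (678.4 − 162.5) × 2^(−(t − 24)/t½) / 678.4

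The protocol states only that the average half-life exceeds 50 h, so I vary t½ from 50 to 100 h.

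| Exit at | t½ 50 h | t½ 70 h | t½ 100 h |
|---|---|---|---|
| 24 h | 76.0% | 76.0% | 76.0% |
| 48 h | 54.5% | 60.0% | 64.4% |
| 52 h (Part 2 discharge) | 51.6% | 57.6% | 62.6% |
| 72 h | 39.1% | 47.3% | 54.5% |
| 96 h | 28.0% | 37.3% | 46.2% |
| 168 h | 10.3% | 18.3% | 28.0% |
| 312 h | 1.4% | 4.4% | 10.3% |

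The time at which half remains is t = 24 + t½ × log2(515.9 / 339.2) = 24 + 0.605 × t½. That is 54 h, 66 h and 85 h for t½ of 50, 70 and 100 h. Collection to 312 h would leave only 1.4% to 10.3% of exposure outside the window.

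**3. Effect on a reported percentage.** With 6 dosed in a part, one missed patient-event is 1/6 = 16.7 points. Sections 3.1 and 4.2.3 allow replacement. If the leaver is replaced, 7 are dosed and the figure is 1/7 = 14.3 points.

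**The case against.** Three stronger readings are tempting, and the documents do not support them.

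- *The early leaver stops being observed altogether.* Known AEs continue to be followed under the four sections cited above. Only the scheduled search for new events stops. Section 4.2.2's sentence on follow-up efforts in every case can also be read as covering all withdrawals, though it gives no end date and no procedure.
- *A serious event after ET could not be reported.* Section 6.1.6.3 requires any AE meeting the SAE criteria to be reported within 24 hours of the site learning of it, and that sentence has no onset cut-off. Section 6.1.6.5 says to report in case of doubt. What is missing is active solicitation.
- *Most of the exposure is still to come for any early leaver.* This holds only for exits before about 54 to 85 h. By Day 8 (168 h) the remainder is 10% to 28%.

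Remaining AUC is also not remaining risk. In healthy subjects tmax was 4 to 7 h, so on those data the peak falls within confinement in both parts. Section 1.3 reports no drug-related AEs up to 30 mg, where AUC0-∞ was 28195 / 678.4 = about 42 times higher. The affected group is small, Section 4.2.1 asks for every effort to retain patients, and the safety analysis is descriptive.

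These points limit the size of the concern but do not close the gap. The reassuring data come from healthy subjects, whereas the study exists to learn about severe CKD and hemodialysis. The protocol itself plans 13 days of safety follow-up for those who stay.

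**Conclusion.** The point holds in a narrow form. No minimum post-dose period is set for seeking new AEs and SAEs in a dosed patient who exits early for a reason other than an AE and can still be reached. Sections 4.2 and 6.1.6.2, read together, end collection on the ET date, while Section 4.2.2 asks for safety follow-up that no schedule provides.

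The effect is conditional: it needs both such a withdrawal and an event afterwards that the site does not hear of. If both occur, the reported percentage is 17 points too low with 6 dosed in the part, or 14 with 7. The exposure figures rest on a ratio of healthy-subject AUCs, mono-exponential decline after 24 h and an assumed half-life of 50 to 100 h. Exposure in the study population is unknown. This is a worthwhile, cheap correction and does not threaten the study's validity.

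A separate, minor wording issue concerns known events. Sections 4.2.1, 6.1.6.3 and 6.1.6.6 describe the end of follow-up differently. Section 4.2.1 covers only AEs that cause discontinuation, so the overlap is partial, but the three should be reconciled.

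**What to change.** - In Sections 3.1 and 6.1.6.2, and in the matching Synopsis text, state that AE and SAE collection runs to Day 14 (312 h postdose) for every dosed patient, including those who terminate early, unless consent to further contact is withdrawn.
- Add a Day 14 telephone contact for AEs and SAEs after ET to Section 4.2.2, footnote 11 of Table 12-1 and footnote 13 of Table 12-2.
- Reconcile Sections 4.2, 4.2.2 and 6.1.6.2, so that the definition of a patient's study duration does not cut off the safety follow-up.
- Separately, align the wording in Sections 4.2.1, 6.1.6.3 and 6.1.6.6 on when follow-up of an ongoing event ends.

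The cost is a few sentences and one call per early-terminated patient in a study of about 12.
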